4.4. Extent of Exposure

Extent of exposure will be summarized by treatment group using the safety analysis set, in terms of treatment duration in cycles and in months, which are calculated as the number of days with dosing record divided by 30.4375 (ie, number of days in a month calculated as 365.25/12).

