Each treatment cycle will consist of 28 days. Participants randomized to placebo, who do not have any evidence of distant metastasis (according to imaging result at Cycle 5 Day 1, as well as at any other relevant unscheduled visit) will be crossed over and start receiving active therapy of apalutamide after completion of 5 cycles of placebo plus ADT treatment. Participants who have PSA progression prior to completion of 5 cycles of study treatment, will cross over to apalutamide at the time of PSA progression. Any participant who develops distant metastatic disease will discontinue study treatment and may receive subsequent therapy according to standard of care. Around half of the participants in the placebo arm are expected to have documented PSA progression after completion of 5 cycles treatment, as estimated from the ARN-509-003 study data, and would therefore, allow sufficient time for the evaluation of TTPP and comparison between apalutamide and placebo.

During the treatment phase, PSA will be collected and analyzed by a central laboratory but investigators, participants, and the study team will be blinded to the results until completion of the study or the sponsor decides to unblind the study at final analysis. The central laboratory will analyze the individual PSA data, collected at baseline and post-baseline obtained within the first 5 cycles to flag out documented PSA progression per PCWG2 and the data will be entered into the interactive web response system (IWRS) to trigger the cross-over by an independent team not affiliated with the study team. The cross-over of control arm participants will be handled by IWRS to maintain the blinding of original treatment assignment of individual participant.

Participants will be followed for safety and efficacy as per Schedule of Activities (SoA) and will remain on study treatment until development of distant metastases as assessed by investigators or the development of unacceptable toxicity or the end of study defined as the time at which the MFS events are observed in approximately 60% of the study population or 3 years after the final analysis for the primary endpoint (TTPP), whichever comes first.

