6.4. Study Intervention Compliance

At each clinic visit, participants will be asked to return any remaining study drug from the previous dosing cycle as well as all used and unused study drug containers.

Treatment compliance will be defined as the number of tablets taken divided by the expected number of tablets and reported as percentage. In case of dose reductions, the expected number of tablets will reflect the new dose level. Tablets that are not returned will be considered to have been taken, unless otherwise specified in the eCRF.

The investigator or designated study site personnel will be responsible for providing additional instruction to any participant who is not compliant with taking the study drug. In the absence of toxicity, if the dosing compliance is not 100%, then investigators or designated study site personnel should re-instruct participants regarding proper dosing procedures and the participant may continue study treatment.

The study site must maintain accurate records demonstrating dates and amount of study drug received, to whom dispensed (participant-by-participant accounting), and accounts of any study drug accidentally or deliberately destroyed. At the end of the study, reconciliation must be made between the amount of study drug supplied, dispensed, and subsequently destroyed or returned to sponsor or its representative.

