2. GENERAL ANALYSIS DEFINITIONS

Study Day is calculated in reference to the date of randomization for efficacy analyses and date of first dose for safety analyses (efficacy analysis Study Day 1 = date of randomization; safety analysis Study Day 1 = date of first dose). Positive study days will count forward from Study Day 1. Study Day -1 will be the day before Study Day 1, and all subsequent negative study days will be measured backward from Study Day -1. There will be no Study Day 0.

The first dose starts on Day 1 of Cycle 1.

Unless otherwise specified, baseline value is defined as the closest measurement prior to the first dose of study drug. Change from baseline will be defined as (post-baseline value – baseline value).

Treatment Duration is calculated as the duration of time from the date of the first dose of study drug to the date of last dose of the study drug, ie, date of last dose – date of first dose + 1.

Time to Event is calculated as the number of days from randomization to the date of the event of interest, ie, date of event of interest – date of randomization + 1. Time to event endpoints will be based on the actual date of the event, not visit number or visit label.

Continuous/numerical variables will be summarized using mean, standard deviation (SD), median, minimum, and maximum. Categorical variables will be summarized using count and percentage. In general, means and other measures of central tendency will be displayed with one more decimal digit than collected, and standard deviations and other measures of variability will be displayed with two decimal digits more than collected. For frequency counts of categorical variables, categories for which the counts are zero will be displayed for the sake of completeness. For example, if no subject discontinued due to "withdrawal of consent", this reason would still be included in the table but with a count of 0.

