4.3. Treatment Compliance

Treatment compliance and dose modifications will be summarized by treatment group using the safety analysis set.

Treatment duration will be defined as the duration of time from the date of the first dose of study drug to the date of last dose of study drug + 1 day.

Drug compliance will be summarized by the treatment group and the percent treatment compliance will be defined as the number of tablets taken during the study divided by the expected number of tablets, multiplied by 100. The number of tablets taken will be calculated based on the number of tablets dispensed minus the number of returned tablets. A subject's expected number of tablets will be calculated according to the planned treatment regimen. For example, for subjects with no dose modification the expected number of tablets equals the number of assigned tablets per day multiplied by treatment duration, however for subjects with dose reduction the expected number of tablets will be smaller. Subjects with at least one dose reduction or with dose interruption and the reason for the dose modification will be summarized by treatment group.

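### SAP 4.4 applies a days-per-month divisor to exposure in cycles, and uses the term treatment duration for a different quantity from SAP 2 and 4.3

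*SAP*

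**What the plan says.** SAP 4.4 (Extent of Exposure) summarises exposure by treatment group on the safety analysis set, as "treatment duration in cycles and in months, which are calculated as the number of days with dosing record divided by 30.4375". It explains the divisor as the "number of days in a month calculated as 365.25/12". No other rule for cycles is given there.

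Protocol 4.1 fixes the cycle length: "Each treatment cycle will consist of 28 days".

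SAP 2 defines treatment duration as the "duration of time from the date of the first dose of study drug to the date of last dose of the study drug", computed as last dose minus first dose plus 1. SAP 4.3 repeats this: "Treatment duration will be defined as the duration of time from the date of the first dose of study drug to the date of" the last dose, with one day added. Both are calendar spans, so days on which dosing was interrupted are included.

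**The concern.** There are two separate defects in one sentence.

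- **Unit.** Cycles and months share one formula whose divisor is explicitly a month. A cycle count needs a 28-day divisor. Five cycles matter in this design because that is the maximum placebo period before cross-over. Under the rule as written, a man who completes all five without interruption cannot appear in the exposure table as having had five.
- **Definition.** The term treatment duration means a first-to-last-dose span in SAP 2 and 4.3, but a count of dosed days in SAP 4.4. A programmer working from 4.4 and one working from 2 or 4.3 would produce different values for any man whose dosing was held.

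Safety and tolerability is a secondary objective, and protocol 9.3.2 lists exposure to study drug among the safety tabulations. These tables are what a reader uses to interpret adverse event incidence, so their units and definitions should be right.

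**Working it through.** **Inputs**
- Divisor 30.4375, SAP 4.4.
- Cycle of 28 days, protocol 4.1.
- Maximum placebo period of 5 cycles, protocol synopsis: 5 × 28 = 140 days.
- Hold of up to 28 days for rash, in either arm, protocol 6.6.1. It is used here only to illustrate size. Holds of 14 and 56 days are added as assumptions to show the range.
- 13 cycles (364 days) as a longer illustration.

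**Step 1. Reproduce the plan's figure.** 365.25 / 12 = 30.4375. The divisor is correct for months.

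**Step 2. Cycles, uninterrupted dosing.** As written: days / 30.4375. With the protocol's cycle: days / 28.

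| Days | As written | Days / 28 |
|---|---|---|
| 140 | 4.60 | 5.00 |
| 364 | 11.96 | 13.00 |
| 728 | 23.92 | 26.00 |

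The ratio is always 28 / 30.4375 = 0.920, a shortfall of 8.0%. It depends on neither arm nor duration.

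**Step 3. Months, dosed days versus span.** SAP 4.4: (span − held days) / 30.4375. SAP 2 and 4.3, expressed in months: span / 30.4375.

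| Span (days) | Held (days) | SAP 4.4 | SAP 2 / 4.3 | SAP 4.4 lower by |
|---|---|---|---|---|
| 140 | 0 | 4.60 | 4.60 | 0% |
| 140 | 14 | 4.14 | 4.60 | 10% |
| 140 | 28 | 3.68 | 4.60 | 20% |
| 140 | 56 | 2.76 | 4.60 | 40% |
| 364 | 28 | 11.04 | 11.96 | 7.7% |

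The relative gap is held days / span, for example 28 / 140 = 20% and 28 / 364 = 7.7%.

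**Step 4. Both together, in cycles.** For 140 days with a 28-day hold, SAP 4.4 as written gives 112 / 30.4375 = 3.68. The span gives 140 / 28 = 5.00 and dosed days give 112 / 28 = 4.00. The printed figure matches neither sensible definition.

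**Step 5. Does SAP 4.4 feed anything else?** SAP 4.3 computes compliance as tablets dispensed minus returned, over expected tablets, using its own first-to-last-dose duration. Neither the 30.4375 divisor nor the dosed-day count enters. TTPP runs from randomization to PSA progression and does not use exposure.

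**The case against.** **The divisor was meant for months only.** The parenthesis describes it as a month, so the author may simply have left out the cycle rule. That is plausible, but then the SAP promises an output in cycles with no rule for it. The sentence needs amending on either reading.

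**Dosed days are a legitimate exposure measure.** This stands. The dosed-day figure in months is not wrong in itself; the defect is two quantities under one name. Interruptions and their reasons are also summarised under SAP 4.3, so holds remain visible. The 20% gap is an unfavourable illustration: it puts the longest listed rash hold inside the short placebo period, and over 364 days the same hold gives 7.7%.

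A reader might also infer three stronger points, which the documents do not support.

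- **That compliance is misstated, so that a man held as directed shows 80%.** SAP 4.3 offers the product of tablets per day and duration as an example for men without dose modification, and the same paragraph treats interruption as a modification. It then says that "for subjects with dose reduction the expected number of tablets will be smaller"; protocol 6.4 likewise says "In case of dose reductions, the expected number of tablets will reflect the new dose level". Neither addresses holds. At 4 tablets a day over 140 days with a 28-day hold, compliance is 448 / 560 = 80% if held days count as expected, and 448 / 448 = 100% if they do not. The rule is unspecified; 80% is only one reading.
- **That the errors are worse on apalutamide.** The divisor error is the same 8.0% in both arms, and the hold rules cover apalutamide and placebo alike. Only the dosed-day gap could differ by arm. The global study's 26% versus 6.3% are rash incidences, not hold rates, and under protocol Table 4 Grade 1 rash without symptoms does not lead to a hold.
- **That placebo exposure would absorb the apalutamide period after cross-over.** SAP 2.3.2 assigns men in the safety set by treatment actually received, protocol 9.3.2 lists exposure with the safety tabulations, and the SAP Safety section sets out separate columns before and after cross-over. A cross-reference from 4.3 and 4.4 would be tidier, but its absence is not an error.

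**Conclusion.** The point holds for the exposure table. Taken literally, SAP 4.4 understates exposure in cycles by a constant 8.0%, whatever the arm or duration. It also gives treatment duration a meaning that conflicts with SAP 2 and 4.3. That conflict has no effect without holds and an effect equal to the held fraction of the span otherwise, 10% to 40% for 14- to 56-day holds in 140 days.

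The 8.0% rests on the literal reading that one formula serves both units; on the other reading the cycle rule is missing. The hold figures are illustrations, since the documents give no expected frequency or length of holds in this trial. The consequence is limited to descriptive tables. No hypothesis test, power figure or compliance percentage changes because of SAP 4.4.

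**What to change.** In SAP 4.4:
1. Divide by 28 for cycles and by 30.4375 for months.
2. Take treatment duration as last dose minus first dose plus 1, as in SAP 2 and 4.3.
3. Report days with a dosing record under a separate name, such as days dosed.

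Two clarifications are optional: state in SAP 4.3 how documented hold days enter the expected tablet count, and cross-reference the four safety columns from SAP 4.3 and 4.4.

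The cost is SAP wording and a few lines of table programming. No new data are needed, because the calculation uses dosing dates and records that the plan already relies on. The protocol need not be amended.

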4.5. Protocol Deviations

Protocol deviations will be summarized by treatment group using the ITT. Protocol deviations will be reviewed on a case-by-case basis and major protocol deviations (including COVID-19 related) will be identified and summarized by the following example categories:

- Deviation from inclusion/exclusion criteria
- Received wrong treatment or incorrect dose
- Received disallowed concomitant treatments
- Other

The categories will be finalized prior to database lock.

If warranted, the protocol deviations that are specifically related to inclusion/exclusion criteria will also be summarized.

COVID-19 related protocol deviations will be listed.

4.6. Prior and Concomitant Medications

Prior and concomitant medications will be summarized by treatment group, World Health Organization (WHO) Drug therapeutic class, and generic medication name using the safety analysis set. Prior medications are those taken (with medication start date) prior to Cycle 1 Day 1. Concomitant medications are those, other than medications involved in experiment, taken during the Treatment Phase, ie, with medication start date on or prior to the 30th day after the last dose of study drug and medication stop date on or after Cycle 1 Day 1 or ongoing.

Subsequent prostate cancer therapies received after the Treatment Phase will be summarized by treatment group using the efficacy analysis set. If the therapy is medication, then it will also be summarized by WHO Drug therapeutic class and generic medication name.

5. EFFICACY

The following section outlines the planned analyses of the primary, secondary efficacy, and the exploratory efficacy outcomes of the study.

Efficacy analyses will be performed using the ITT population, incorporating the randomization stratification factor as documented on the IWRS, unless otherwise specified.

Time-to-event endpoints will be summarized using the Kaplan-Meier method and displayed graphically where appropriate.^[3] Median event times and 2-sided 95% confidence interval for each median will be provided. Cox proportional-hazard models, including the stratification factor at baseline, will be used to estimate the hazard ratio (HR) and its 95% confidence interval (CI) for TTPP.

Response endpoints (e.g. PSA response rate) will be summarized using descriptive statistics for categorical data by treatment group. The relative risk (treatment:control) will be reported along with the associated 2-tailed 95% CIs. The two treatment groups will be compared using the stratified Mantel-Haenszel test if data warranted; Fisher's exact test may be used if the expected counts in some cells are small.

5.1. Analysis Specifications

All efficacy endpoints will be summarized by treatment group using the ITT. When stratified analyses are performed, strata used by the interactive web response system (IWRS) during subject randomization will be used unless otherwise specified.

5.1.1. Level of Significance

In general, a two-sided significance level of α =0.05 will be used for all hypothesis testing and all confidence intervals will be calculated on the two-sided 95% confidence level (CI), unless otherwise specified.

5.2. Primary Efficacy Endpoint

The primary endpoint is time to prostate specific antigen (PSA) progression (TTPP, as defined by Prostate Cancer Working Group 2 [PCWG2])

5.2.1. Definition

Time to prostate specific antigen progression (TTPP) - defined as the time from randomization to the first date of documented PSA progression based on Prostate Cancer Working Group 2 (PCWG2) criteria.

Apalutamide group subjects will be censored at the last date of PSA assessment if not PSA progressed at the time of analysis. For the control group, subjects who switched treatment and had not yet PSA progressed at that time will be censored at the date treatment switching. For all randomized subjects who received anticancer subsequent therapy before PSA progression documented, the TTPP will also be censored at the last date of PSA assessment prior to the start of subsequent therapy.

5.2.2. Estimand

Population:

Subjects with high-risk (defined as PSA Doubling Time (PSADT) ≤10 months) Non-Metastatic Castration-Resistant Prostate Cancer (NM-CRPC).

Variables:

Time to Event: TTPP

Intercurrent Events and Strategies (Table 1):

Analysis	Variable	Intercurrent Events	Strategies
Primary	TTPP	Treatment switching: censoring those subjects who are event-free when treatment switching at the date of occurrence of intercurrent event, regardless if the subjects experienced the event of interest afterward	Hypothetical strategy
		• Death: censoring those subjects that are event-free at the last date where it is known the patients have yet to experience the event of interest to estimate the hypothetical estimand as if we had observed all patients until their endpoint event	Hypothetical strategy
		Subsequent anti-cancer therapies: censoring those subjects who are event-free at the last date where it is known the patients have yet to experience the event of interest prior to the start of occurrence of intercurrent event	Hypothetical strategy

Population level summary:

Survival endpoint of TTPP: log-rank test and hazard ratio between the two treatment groups with stratification if data warranted.

5.2.3. Analysis Methods

The final analysis of TTPP will be performed at approximately 5 months after last subjects dosed.

The distribution of TTPP will be estimated using the Kaplan-Meier (KM) method. Median TTPP, as well as PSA progression free rate at selected timepoints, and the corresponding confidence interval will be reported with Kaplan-Meier curves. The comparison of TTPP between the 2 treatment groups will be based on log-rank test stratified, if data warranted, by the randomization stratification factor (PSADT [>6 months vs. ≤6 months]). The hazard ratio and corresponding confidence interval will be estimated using a Cox proportional hazards model stratified, if data warranted, by aforementioned randomization stratification factor.

The proportional hazard assumption will be assessed graphically by plotting log(-log[estimated survival distribution function]) against log(survival time). The resulting graphs should have approximately parallel lines when the assumption holds. If the proportional hazard assumption is reasonably met, then the HR will be used as an estimate of treatment effect. If the proportional hazard assumption is considered violated, then the statistical comparison between survival distributions remains valid, but treatment effect may only be evaluated using the median time to event in each treatment group.

Non-stratified log-rank test may be performed as sensitivity analyses to evaluate the robustness of TTPP analysis results if stratified test is warranted by the data.

Finally, to assess the consistency of treatment benefit across subgroups for TTPP, a forest plot of estimated hazard ratios, and associated 95% CIs will be provided for subgroups defined in Section 2.4. To estimate the HR, and CI in each subgroup, the Cox proportional hazard model will be univariate (i.e., including only treatment group).

Missingness of PSA assessment due to COVID-19 will be summarized to evaluate COVID-19 impact on disease assessment.

5.3. Secondary Endpoint

• Prostate-specific antigen (PSA) response rate (as defined by PCWG2).

5.3.1. Definition

Prostate-specific antigen (PSA) response rate is defined as the proportion of subjects who achieved at least a 50% decline in PSA value from baseline assessed by a central laboratory according to PCWG2 criteria. The PSA response will be confirmed by a central laboratory measurement obtained 4 or more weeks later. Placebo group subjects who do not have PSA response at the time of treatment switching will be considered as non-responder.

5.3.2. Analysis Methods

PSA response rate will be summarized by treatment group. The relative risk (treatment:control) will be reported along with the associated 2-tailed 95% CIs. The two treatment groups will be compared using the stratified Mantel-Haenszel test if data warranted. Fisher's exact test may be used if the expected counts in some cells are small.

Summary tables and waterfall plots describing change in PSA relative to baseline will be reported at 12 weeks (or earlier for those who switch/discontinue study treatment prior to 12 weeks). PSA response by Week 12 will also be reported by treatment group.

5.4. Exploratory Efficacy Variables

Efficacy Variables

- Metastasis-free survival (MFS)
- Overall survival (OS)
- Time to symptomatic progression

5.4.1. Definition

- Metastasis-free survival (MFS) defined as the time from randomization to first evidence of investigator determined radiographically detectable bone or soft tissue distant metastasis (simply referred to as "metastasis" from this point forward) using the Response Evaluation Criteria in Solid Tumors (RECIST v1.1) or death due to any cause (whichever occurs earlier). For new bone lesions detected on bone scans, a second imaging modality (e.g., CT or MRI) will be required to confirm progression.
- Overall survival (OS) defined as the time from randomization to date of death from any cause
- Time to symptomatic progression will be defined as the time from randomization to documentation in the CRF of any of the following (whichever occurs earlier) + 1 day:
 - Development of a skeletal-related event (SRE): pathologic fracture, spinal cord compression, or need for surgical intervention or radiation therapy to the bone.
 - Pain progression or worsening of disease-related symptoms requiring initiation of a new systemic anti-cancer therapy.
 - Development of clinically significant symptoms due to loco-regional tumor progression requiring surgical intervention or radiation therapy.

Adverse event, concomitant medication, or survival follow-up CRFs may also be the source of these findings.

Time to symptomatic progression for patients who do not experience any of the events described above will be censored on the date on which they were last known to be event-free.

